## Approach

**Overall Strategy:** The primary aim of this application is to investigate relationships of risk factors to the development of PPP at 6 mo following TKR, through independently predictive and mediated models. These risk factors are preoperative thermal pain sensitivity, pain anxiety and catastrophizing; postoperative area of secondary mechanical hyperalgesia or hypoalgesia (numbness) and pain intensity. **PPP** for this study will be defined as "**pain in the operated knee at six months after TKR, with other causes of pain excluded and reported intensity on 0-10 NRS scale of  $\geq 4$ .**" The study will also evaluate the relationship of PPP incidence with the severity of functional impairment. This is a single-site prospective clinical investigation of 300 consented OA patients undergoing primary, unilateral TKR. Although we realize the importance of genetic susceptibility on the development of PPP, the complexity of determining the multiple genes that may contribute to this condition is beyond the scope of this proposal. However, prior to surgery we will obtain a blood sample (8.5 mL) from all patients, process it for DNA analysis, and store at -80° C for future studies by [name], NINR (letter of support) to screen for genetic predictors of PPP, such as COMT and GCH1. We will also obtain three blood samples (5ml each) for RNA analysis. In a previous IRB approved study, we also obtained blood samples for RNA analysis prior to hip replacement surgery and 24 hours afterward and found that IL18R1 was up-regulated while IL-8RB was down-regulated and may be related to the normal acute post

operative inflammation. However, we now need to examine the changes in cytokine gene expression in the TKR patients. All of the blood samples will be sent for analysis to [name] laboratory. The patients' genetic information will stay confidential, and will be identified by a study number, and not a name. This information will not be disclosed to any other third party. Personal data will be stored at Rush University Medical Center. The samples sent to [name] laboratory will be appropriately coded so that the patient's name does not appear on the samples. Data will be kept for 1 year from the time the last patient is enrolled in the study.

Study Calendar	Preop	Post-Incision				Post-operative			
		24h	36h	48h	72h	3 wk	6 wk	3 mo	6 mo
General Physical Examination	X					X	X	X	X

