contacted and the epidural infusion titrated (per previous published protocol). However, if these measures fail and the patient has severe pain, intravenous opioids (morphine 2 mg bolus) will be administered. Records will be kept of the total amount of epidural solution consumed, including morphine boluses, in increments of 4h for the 24h postoperative period. After 24 hours, the epidural catheter will be removed. We customarily administer warfarin (oral 5 mg) for deep venous thrombosis prophylaxis on the night of TKR. An International Normalized Ratio will be obtained prior to removing the catheter. Once the epidural catheter is removed, all patients will receive hydrocodone 10 mg/acetaminophen 325 mg, 1-2 tablets every 4-6h depending on the NRS pain score for a maximum of 6 tablets/ day (to keep within current geriatric guidelines <3.25 mg/day acetaminophen), until discharged from the hospital. Patients having NRS  $\geq 4$  for more than 1h will receive intravenous morphine 2-4 mg as needed every 15 min for a maximum of 15 mg over a period of 2h. Patients allergic to intravenous morphine or oral hydrocodone will receive an equivalent dose of intravenous hydromorphone or oral oxycodone respectively. All analgesics administered over 0-72h will be recorded in the data collection book for inclusion as covariates in analyses. Although a more complex algorithm for pain management, including multimodal non-opioid analgesia, could be used and continued for at least 2 wks later, those analgesics might become factors themselves that influence the development of PPP, and therefore will not be used in this proposed study. We will also obtain a 5mL blood sample for RNA analysis during the hospital stay (when wound inflammation is maximum).

[figure not shown]
**Postoperative Management:** Routine vital signs will be recorded on the floor and transferred to the data collection book. The patients will undergo routine physical therapy sessions twice/daily until they meet the hospital discharge criteria as determined by the therapist.

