#### **Long-term Assessments (same methods used pre-surgery):**

(1) **Pain Intensity:** NRS of the operated knee will be obtained by RN from the patients at the 3 wk, 6 wk, 3 mo and 6 mo scheduled visits.

(2) **Neurophysiologic Assessment** will be performed at the 6 mo scheduled visit.

(a) *Examination of the knee for peripheral neuropathic pain (StEP)*

(3) **Psychosocial Measures:** Beck Depression Inventory will be administered at 6 mo by RN.

(4) **Functional Measures:** ROM, WOMAC and SF-36 questionnaires will be administered at 3 wk, 6 wk, 3 mo and 6 mo.

(5) **Skin Temperature:** Skin temperature will be performed at 6 months

**Patients who have NRS $\geq$ 4 at three wks and beyond:** For patients having NRS $\geq$ 4 at 3 wk and beyond, the oral opioid regime will be continued. If the hydrocodone/acetaminophen regime does not maintain a NRS $<$ 4, then oral long-acting opioids such as time-release oxycodone 10 mg twice/day will be prescribed. The purpose of closely following the analgesics and NRS for the study patients is to ensure that at the 6-mo time point the analgesic consumption is within a standard protocol for all patients, whether they do or do not have PPP. Patients who have persistent pain at the 3 and 6-mo visits will be evaluated by the orthopedic surgeon for prosthetic-related failure. An examination will be performed to evaluate instability of the tibial femoral joint or patellar maltracking. Plain radiographs will be reviewed by the orthopedic surgeons (Co-investigators) for evidence of prosthetic loosening, malposition and patellar maltracking, as well as overall axial alignment to ensure coronal alignment is within the range of neutral to 10 deg of valgus. If this evaluation is negative, an erythrocyte sedimentation rate (ESR) and C-reactive protein (CRP) measurement will be obtained as a screening tool for infection. If these indices are abnormal (ESR $>$ 30 mm/h; CRP $>$ 10 $\mu$ g/mL), an aspiration of the knee will be performed, including a synovial fluid white blood cell count with differential and culture to rule

out infection. These parameters are based on previous work by [name] (Co-investigator) in this specific topic.

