**General statistical analysis:** Descriptive statistics will be reported as mean and standard deviation (SD) for continuous normally-distributed variables, and reported as counts and percentages for dichotomous variables. Assumptions will be evaluated and, if violated, either corrective measures will be taken (data-transformation) or other less restrictive methods will be implemented. Error inflation for multiple pre-planned comparisons will be corrected by using the Bonferroni step-down method. Models will be examined with no risk factors, with individual risk factors, and with multiple risk factors. The distribution of the primary outcome, NRS pain scores at 6 mo, will be evaluated, transformed to normal and then modeled as a continuous variable. If this is not possible, *then the dichotomous version*, as defined for PPP, will be used. We expect that the primary outcome of PPP (dichotomous) will be modeled using a logistic regression because the distribution of NRS pain scores from our preliminary survey data was strongly bi-modal (modes:0, 3). Thus it appears that this kind of distribution represents two distinct populations (a normally distributed pain population and a unimodal 'no-pain' population). Pain intensity (continuous) will be separately modeled for those patients who report a non-zero pain level. Risk factors will be evaluated, for **independent** association with the outcome variable, first for linearity and then for model fit using backward stepwise logistic regression (criterion  $P<0.05$ ). Model fit will be assessed by the Hosmer-Lemeshow test and validity of the fit models and predictive accuracy will be assessed using bootstrapping methods as well as the AUC 'c-index'. Analysis will also be performed on the raw NRS score (at 6 mo) using general linear models and mixed model regression as this may elucidate additional details about relationships among the factors and how they relate to pain at 6 mo. **Mediation** models will be evaluated based on techniques pioneered by Baron and Kenny, but with the modification of bootstrapping techniques to produce multiple mediator results with confidence intervals. Sobel method and  $R^2$  effect-size measures will be used to test and evaluate the mediation effects as well. Distributional assumptions and

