model fit will be evaluated for all models. **Moderating** effects will be tested using model building with predefined interactions for linear or logistic models.

Due to the extensive monitoring designed into our protocol we do not expect a large amount of missing data; however, the missing data that does arise will be handled using multivariate multiple imputation. Data not assumed to be missing at random, will be evaluated for systematic effects using sub-groups stratification. Statistical analyses will be performed using SAS version 9.1 (SAS Institute Inc, Cary, NC) or SPSS (SPSS for Windows, Rel. 16.0.1. 2007. Chicago: SPSS Inc.), with statistical significance determined with a Type I error threshold of  $\alpha = 0.05$ . For continuous outcome mediation analysis we will use a SAS macro (INDIRECT macro) and for dichotomous outcomes the SPSS macro version (INDIRECT macro) will be used, as the SAS macro version does not allow for dichotomous outcome variables.

**Primary endpoint:** The *primary endpoint* for the **Primary Aim** will be the incidence of PPP after TKR (similar to our power analysis), evaluated at 6 mo. For the **Secondary Aims**, the *primary endpoint* will be functional outcomes (ROM, WOMAC, SF-36,).

**Secondary endpoints:** The *secondary endpoint* for the Primary and Secondary Aims will examine additional parameterizations of PPP at 6 mo (NRS pain non-dichotomous, StEP neuropathic pain examination). Use of raw NRS pain scores may highlight functional (e.g. linear) relationships between pain and the predictive factors. Analysis will be performed as described for the primary outcome variable (incidence of PPP) but with the re-parameterized outcome variable and different model assumptions, depending on distributional properties. Each re-parameterization will be evaluated with respect to and compared with the primary outcome.

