**Covariates:** Preoperative covariates included are as follows: age, weight/BMI, OA severity and ASA status. Perioperative covariates include: postoperative analgesic consumption and duration of surgery. Complications after TKR will be recorded and included as a summed incidence. Patient questionnaires of drug use in the first three wks postoperatively will be converted to daily morphine equivalents and included as a covariate in the predictive models. Although the protocol stipulates uniformity in medication use during the acute postoperative period, once the patient leaves the hospital, their analgesic use over the next 6 mo cannot be rigidly controlled. To reduce variation we will prescribe analgesics as needed (per protocol above mentioned) and will remain in contact with the patients to record additional medication.

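### The complications covariate has no end date, so it can absorb findings from a work-up done only in patients with pain at 3 and 6 months

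*Combined protocol and SAP*

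**What the plan says.** The Covariates paragraph states: "Complications after TKR will be recorded and included as a summed incidence". It gives no list of qualifying events, no time window and no rule on attribution. Other covariates do have windows. Home drug use is limited, in the same paragraph, to the first three weeks, and the section on the hospital stay says: "All analgesics administered over 0-72h will be recorded in the data collection book for inclusion as covariates in analyses".

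The paragraph on patients with NRS of 4 or more at three weeks and beyond sets out a stepwise search: "Patients who have persistent pain at the 3 and 6-mo visits will be evaluated by the orthopedic surgeon for prosthetic-related failure". It continues: "If this evaluation is negative, an erythrocyte sedimentation rate (ESR) and C-reactive protein (CRP) measurement will be obtained as a screening tool for infection". Abnormal values lead to aspiration and culture.

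The Overall Strategy defines PPP as "pain in the operated knee at six months after TKR, with other causes of pain excluded and reported intensity on 0-10 NRS scale of" 4 or more. The primary endpoint "will be the incidence of PPP after TKR (similar to our power analysis), evaluated at 6 mo".

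Some ascertainment covers every patient. The study calendar has physical examinations at 3 weeks, 6 weeks, 3 months and 6 months and radiograph results at 6 weeks and 6 months. Adverse events are asked about at the contacts between 3 weeks and 3 months. The contacts described for 3 to 6 months name pain and medication but not adverse events.

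Nothing in the document keeps the findings of the pain work-up out of the complications count.

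**The concern.** A covariate meant to explain or predict a 6-month outcome should be fixed before that outcome and should not depend on it. Here a patient in pain is examined more closely than one without pain, at 3 months because of a precursor of the outcome and at 6 months because of the pain that forms part of its definition. An infection, a loose component or maltracking found that way is, in ordinary language, a complication after TKR.

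Two things are at stake. A complications term with no causal role may be reported as associated with PPP. And the c-index, which the plan uses to judge predictive accuracy, may be raised by information that exists only once the outcome is being assessed. That matters because Hypothesis 1 is meant to serve clinical prediction models.

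**Working it through.** The plan gives no figure to reproduce, and no complication or detection rates. What follows is illustration under stated assumptions.

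**1. Incidental findings only.** Inputs: 17.8% PPP (the plan's survey figure); 255 patients (300 less 15% dropout); one true risk factor with log-odds 0.6 per SD (assumed); Poisson complication counts with no effect on PPP. Assumed recorded rates: q0 = 0.08 per PPP-free patient, and q1 per PPP patient as below. There were 1,500 simulated trials per row.

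| q1 | q1/q0 | Count reaches P<0.05 | Mean apparent c-index |
|---|---|---|---|
| 0.08 | 1.0 | 4% | 0.669 |
| 0.15 | 1.9 | 27% | 0.675 |
| 0.20 | 2.5 | 54% | 0.685 |
| 0.30 | 3.75 | 89% | 0.710 |

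Repeat runs of the three unequal rows fell within 23–27%, 50–55% and 87–91%.

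**2. Bringing in the PPP definition.** Step 1 ignores the requirement that other causes of pain be excluded. Suppose a fraction f of the complications recorded in PPP patients explains the pain, and those patients are dropped. The rate among the remaining PPP patients is q1 × (1 − f).

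- f = 1/2: 0.15, 0.20 and 0.30 become 0.075, 0.10 and 0.15, against 0.08 in the PPP-free. P<0.05 falls to 2–5%, 6% and 22–24% in two separate runs.
- f = 3/4: the rates become 0.0375, 0.05 and 0.075, all below 0.08. The Wald test reaches P<0.05 in 0%, 1% and 3%. That test is conservative with such sparse counts, so this does not show absence of bias.
- f = 1: the rate is 0. No PPP case carries a complication, and the coefficient runs to minus infinity (separation).

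The sign changes where q1 × (1 − f) = q0, that is at f = 1 − 0.08/q1, which is 0.47, 0.60 and 0.73 for the three rates. If such patients are recoded as PPP-free instead of dropped, their complications move to the comparison group, which pushes the same way.

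**3. A second construction, by detection probability.** Inputs: the plan's odds ratio of 1.24 per NRS point, SD 2.9 and 259 patients. Assumed: true complication rate 5%, 10% or 20%, unrelated to pain; 90% detected in painful knees, and 20% or 50% otherwise. No patient is excluded from PPP. At a true rate of 10%, recorded rates are 9% against 2%, so the spurious odds ratio is (0.09/0.91)/(0.02/0.98) = 4.8. With 50% routine detection it is (0.09/0.91)/(0.05/0.95) = 1.9.

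- 20% against 90%: P<0.05 in 23%, 52% and 81% of trials at the three true rates; c-index rises from 0.666 to 0.675, 0.683 and 0.702.
- 50% against 90%: P<0.05 in 12%, 19% and 32%; c-index 0.668 to 0.676.
- 90% in both: odds ratio 0.99–1.03, c-index 0.666, P<0.05 in about 3–5%.

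**4. Effect on true risk factors.** With counts driven by 3-month pain at 0.08 against 0.20, the log-odds of the true risk factor moves from 0.522 to 0.516: 0.006/0.522 = 1.1%. At 0.05 against 0.30 it moves from 0.534 to 0.512 (4.1%), and at 0.05 against 0.50 from 0.534 to 0.488 (8.6%). The last two need six- and tenfold differences in recording. In the construction of step 3 the acute-pain odds ratio was 1.86 per SD with and without the complications term.

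**The case against.** The strongest reply is that the outcome definition already deals with these findings. The work-up looks for loosening, malposition, maltracking, instability and infection, which are the obvious other causes of pain, so a positive result may take the patient out of PPP. That defeats any claim that the count will usually appear as a positive risk factor: the upper figures in step 1 need almost no finding in a painful knee to count as another cause. It does not clear the covariate. The same work-up then helps decide both the count and who is a case, and the distortion changes sign.

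Four further points limit the concern.

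- The sentence directly follows the perioperative covariates, so a perioperative window may have been intended. The text does not say so, and a literal reading runs to 6 months.
- All patients are examined and radiographed. This narrows the gap in detection, by an amount the documents do not allow one to estimate. The ESR/CRP, the aspiration and the directed examination remain dependent on pain.
- Some patients in pain at 3 months will be PPP-free at 6 months, which dilutes the contrast.
- A reader might infer that the count will survive backward selection and enter the prediction equation. The General statistical analysis paragraph applies backward selection to risk factors, and complications are not listed among them. The example equation has no complications term, though it is offered only as a simple example.

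**Conclusion.** The concern holds in this form: the window is undefined, and on a literal reading the covariate is partly determined by the outcome or its precursor, in a direction the plan leaves open. This is more than missing detail, because the sign and size of the complications term would depend on how work-up findings are recorded and classified.

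The size cannot be fixed from the documents. Under the assumed rates, the chance that a null count reaches P<0.05 runs from about the nominal 5% to about 90%, and the apparent c-index rises by at most about 0.04 (0.669 to 0.710). With every finding treated as another cause of pain, the term has no finite estimate.

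A reader might go further and infer that the tests of the main risk factors are materially biased. The calculations do not support that: the shift is about 1% at the main assumed rates and nil in the second construction. The damage lies in the complications term and in the accuracy of any model containing it.

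**What to change.** In the Covariates paragraph, limit the complications covariate to events recorded up to a fixed early date that precedes the 3-month pain-triggered work-up and is ascertained in the same way in all patients. Hospital discharge would do, as would the three-week window already used for drug use; the choice is the study team's. Report later complications descriptively by PPP status, and keep them out of the Hypothesis 1, Hypothesis 2 and prediction models.

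This takes one or two sentences and changes no clinical procedure. The cost is that late complications are described and not adjusted for, and a cut at discharge gives up more of them than a cut at three weeks. The change does not settle whether a patient whose work-up finds a cause is coded PPP-free or left out of the analysis; the plan should state that separately.

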### **Detailed Analyses:**

**Primary Aims:** are to investigate the relationships of *risk factors* and the development of PPP at 6 mo post-TKR, through independently predictive (for clinical prediction models, Hypothesis 1) and mediated models (to reveal underlying mechanisms, Hypothesis 2). These risk factors are preop thermal pain sensitivity; anxiety and catastrophizing; postop area of secondary mechanical hyperalgesia and pain intensity.

A. **Independent Risk Factors:** Risk factors will be individually predictive of the PPP (primary endpoint):

*Hypothesis 1 is that greater (↑) preop pain sensitivity, higher levels of preop pain anxiety and catastrophizing, larger areas of secondary hyperalgesia post-TKR and higher postop pain intensity will independently predict increased incidence of PPP at 6 months post-TKR.*

- 1) **Pain Intensity:** Expected Result: (Hypothesis 1): Higher postop pain intensity (↑), will independently predict increased incidence of PPP at 6 mo post-TKR (ex. ↑ postop NRS → ↑ PPP incidence).
- 2) **Neurophysiologic:** Expected Result: (Hypothesis 1): Greater preop pain sensitivity (↑) and larger areas of secondary hyperalgesia ( $\text{cm}^2$ ) post-TKR will independently predict increased incidence of PPP at 6 mo post-TKR (ex. ↑ preop thermal pain sensitivity → ↑ PPP incidence).
- 3) **Psychosocial:** Expected result: (Hypothesis 1): is that greater (↑) catastrophizing (PCS score) will independently predict increased incidence of PPP at 6 months post-TKR (ex. ↑ PCS score → ↑ PPP).
- 4) **Demographics:** Expected result: Patients 65-85 yrs will have a lower incidence of PPP than patients 18-64 yrs.

B. **Mediation Models:** Effects of preoperative factors on development of PPP occur through interrelated neurophysiologic mechanisms:

*Hypothesis 2 is that the effects of preoperative factors on development of PPP occur through interrelated neurophysiologic mechanisms. Thus, it is expected that the area of secondary hyperalgesia post-TKR will mediate links between preoperative pain sensitivity and PPP incidence, as well as mediate links between pain anxiety/catastrophizing and PPP incidence at 6 mo after TKR.*

- 1) **Neurophysiologic:** Expected Result: (Hypothesis 2): Area of secondary hyperalgesia post-TKR will mediate links between preoperative pain sensitivity and PPP incidence: (preop thermal sensitivity score affects area of mechanical secondary hyperalgesia which in turn leads to increased PPP incidence) will fit the data significantly better than the independently predictive model (preop thermal sensitivity score will directly affect PPP incidence).
- 2) **Psychosocial:** Expected result: (Hypothesis 2): Area of secondary hyperalgesia will mediate links between pain anxiety/catastrophizing and PPP (ex. pain anxiety PASS score → area of secondary hyperalgesia → PPP incidence).

**Secondary Aims:** Test for risk moderators.

C. **Moderation Models:** Test for risk moderators:

*Hypotheses 4 postulates that patient age will moderate the relationship between risk factors and PPP development. We expect the predictive relationship between preop pain sensitivity and PPP incidence to be stronger (enhanced) among younger as opposed to older patients*

- 1) **Demographics:** Expected Result: The effect of preop pain sensitivity on PPP will be moderated by age (ex. direct effect is: ↑ preop thermal NRS score → ↑PPP incidence; but moderating effect is: ↑ preop thermal NRS score x ↓age → ↑↑PPP incidence)

**Omnibus Model:** To create a more complete description of the factors, mechanisms and interrelationships involved in development of PPP, several omnibus models will be created and evaluated. Knowledge gained from each of the individual aims will be utilized to create this model, using principal component and factor analysis for variable reduction and predictive modeling with particular focus on mediation between the domains and the aims.

**The prediction equation:** To highlight the risk factors for PPP, including importance (weighting) and interactions, in not only the preoperative phase but in the postsurgical phase, a prediction equation will be described. The use of the prediction equation can then be validated and fine tuned in later studies. A simple example formula for the prediction equation:

$$Pr_i = \frac{1}{1 + \exp(a + \beta_1 Age_i + \beta_2 preOpPainSens_i + \beta_3 SecHyperal_i + \beta_4 postOpNRS_i + \beta_5 TraitAnxiety_i + \beta_6 Catastrophizing_i)}$$

